*Patient flow and feasibility.* Participants will primarily be recruited from local treatment sites currently reporting an overflow of BPD patients; these include the intake and referral offices at Massachusetts General Hospital and the McLean Hospital (see letters of support from clinical faculty at these institutions in Other Attachments). Additionally, participants will be recruited through CARD's general client population. CARD completes over 1000 new patient screenings per year of which approximately 15% endorse symptoms of BPD; rather than refer these individuals out for BPD treatment elsewhere, they will be sent to this study for further assessment. Finally, we will also advertise specifically for the study in locations and publications commonly advertising treatment studies. These recruitment procedures are consistent with a recent data collection at CARD that enrolled 50 individuals with BPD (and comorbid Bulimia Nervosa) over the course of 4 years in the context of an NIMH-funded Career Development Award (PI: [name]). Further, while recruiting for a small pilot study, 4 patients meeting the current study's eligibility criteria were recruited from the above sources in a two-month period (2 from CARD, 1 from McLean Hospital, and 1 from Massachusetts General Hospital). Recruitment at this rate during the proposed project would be sufficient to achieve enrollment goals.

*Participant Retention:* In both phases, participants that discontinue will be replaced. However, we will employ procedures during both study phases to reduce potential dropout. First, at the baseline assessment, the PI will personally meet with participants to provide them with a plan for discussing any concerns as they arise throughout the study. Specifically, participants will be informed that they should first address concerns directly with study staff (IEs) or the PI. In cases where patients may not feel comfortable addressing the PI directly, [name] (the mentor on this study and Director Emeritus of the clinic) may be involved to resolve concerns with patients. This will establish a positive working alliance with the research "team." Additionally, study staff will be flexible in re-scheduling missed sessions within reasonable limits. These procedures recommended by Marsha Linehan and others involved in treating patients with BPD and co-occurring disorders and will be overseen by [name], a close collaborator on this project with

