**PHASE II: Multiple Baseline with Phase Change Procedures:** Participants (8) will be randomized to a 2- or 4-week initial baseline period. The baseline period will consist of assessment only, described in detail below. Following the initial baseline period, participants will receive 4 weekly 50-minute sessions of an intervention; this duration of treatment is consistent with clinical experience at our center indicating that this is an adequate amount of exposure to given UP modules. The Countering EDBs Module from the UP will be used as the basis for session content as the modular approach of the UP allows for the delivery of just this treatment topic isolation. Randomization to baseline phases of differing lengths will allow us to explore whether change on variables of interest occurs when and only when the intervention is applied. *Phase II Treatment Quality Assurance.* The PI (applicant) will serve as the study therapist. The PI is a licensed clinical psychologist with over eight years of experience with adults with BPD. Additionally, the PI is fully certified as an expert in the delivery of the UP. All therapy sessions will be audiotaped and will all be rated for adherence and competence ratings by an expert rater. Most importantly for the current project, integrity measures will assess for allowed and disallowed techniques within the UP to ensure only information regarding countering EDBs is presented as a means to isolate this putative mechanism. Descriptive statistics on fidelity measures will be obtained.

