*Phase II Assessment.* During all periods (baseline and intervention), participants will be asked to complete a daily log of EDBs and emotional intensity using SymTrend, a software developed specifically for real-time data collection. Participants will be trained in using their personal smart-phone to complete these daily logs on SymTrend. Participants who do not own a smart-phone will be excluded from this study; based on consultation with collaborator [name] who routinely conducts research using EMA and recent studies utilizing these methods at CARD, we anticipate very few participants will be excluded do to this criterion. Participants will be asked to self-initiate an entry whenever they are experiencing strong emotions (at least once per day) and will be asked to rate the intensity of their emotional experience. One hour after self-initiating the entry, participants will be prompted by text message via SymTrend to indicate whether they engaged in EDBs or acted inconsistent to emotional urges, as well as to rate their current emotional intensity. SymTrend will automatically send text messages everyday at mid-day to remind participants to self-initiate entries when feeling a strong emotion. Additionally, participants will receive a text-message reminder once a week prompting them to complete a longer self-report battery. Participants will have the option to complete the logs and questionnaire battery on a computer rather than smart phone, should they prefer. Phase II assessment measures will include: **Diagnostic Measures.** As in Phase I, the DIPD-IV and ADIS-5 (described above) will be used to confirm inclusion and exclusion criteria. **Major Assessment Measures.** Major assessments will be completed at four time-points: pre-baseline period, pre-intervention period, post-intervention, and post-follow up. These assessments will include: (1) Zanarini Rating Scale for Borderline Personality Disorder (ZAN-BPD). The ZAN-BPD is a continuous clinician-rated scale designed to address change in BPD symptoms by rating severity of the diagnostic criteria across a 1-week time frame. The ZAN-BPD has demonstrated high levels of reliability and validity. (2) Paced Auditory Serial Addition Task- Computerized Version (PASAT-C). The PASAT-C is behavioral measure that has been used with BPD participants as assess willingness to engage in goal-directed behavior while experiencing distress and will be used as a behavioral indicator of acting inconsistent with EDBs. **Weekly Measures.** As noted above, patients will be prompted to complete a self-report battery via text-message from SymTrend on a weekly basis. The battery will include the (1) self-report version of the ZAN-BPD (ZAN-BPD-srv) and the (2) Multidimensional Experiential Avoidance Questionnaire (MEAQ). The MEAQ is a self-report measure that will be used to assess emotional tolerance. The MEAQ has demonstrated high internal consistency and validity. Finally, (3) changes in medication will be tracked. **Daily Measures.** As described above, participants will be asked to self-initiate entries when experiencing a strong emotion. These entries will involve completing the PANAS-X and then, one hour later, completing a series of structured questions regarding engagement in EDBs, followed by an additional PANAS-X.

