*Phase II Data Analyses:* The multiple baseline and phase change design will make between- and within-subjects analysis possible. By applying different baseline lengths across individuals, between-series comparisons will be possible to determine if changes in EDBs, emotional intensity, and emotional tolerance occur when and only when the intervention is applied. The phase change (baseline phase to treatment phase) process will allow for within-series comparisons to examine concomitant changes in EDBs, emotional intensity, and emotional tolerance when treatment is present compared to when it is absent within individuals. For both between-and within-subjects comparisons, we will first plot parallel lines representing changes in these variables over time for each individual. These will be directly compared in terms of changes in level and slope to determine if differences seen are due to phase change. We will also conduct non-parametric randomization tests of mean differences in EDBs, emotional intensity, and emotional tolerance as a function of phase using the SCRT within the R statistical framework. Results from these tests will be used with visual inspection of data to draw conclusions regarding effects of the intervention on frequency of EDBs, emotional intensity and emotional tolerance. We will also explore maintenance effects of our intervention by examining stability in EDBs, emotional intensity, and emotional tolerance during the follow-up phase. Finally, as an exploratory analysis, we will examine phase effects (baseline, treatment, follow-up) on clinician rated and self-reported BPD symptoms.

*Phase II, Hypothesis I:* Individuals will demonstrate change in self-reported frequency of EDBs, intensity of emotion (PANAS) and tolerance of emotions (MEAQ), as well as behavioral willingness to act inconsistent with emotional urges (PASAT-C) only after treatment is applied. *Phase II, Hypothesis II:* Change in these variables will be maintained during a 4-week follow up period. *Phase II, Hypothesis III:* In this exploratory analysis, we hypothesize that clinician-rated and self-reported BPD symptoms (ZAN-BPD, ZAN-BPD-srv) will decrease when and only when the intervention is applied, and only for patients who demonstrate reduction in EDBs.

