*Power Analyses.* Sample size in SCEDs refers to the number of observations collected. In Phase I, 35 observations (ratings of emotional intensity) will be collected for each emotion under study (18 acting consistent with emotional urges and 18 acting inconsistent); this will yield 180 total observations with 90 in each condition. Phase II will result in 88 observations for weekly measures and 616 observations for daily

measures. These numbers of observation will make possible detection of medium effect sizes across both phases.

**Timeline Timetable:** Support is requested for 4 years in order to successfully complete both phases of the project, which are integral to the applicant's training goal to gain expertise in exploring mechanisms of action in treatment. Year 1 of the project will be dedicated to acquiring advanced training in the assessment of physiological and behavioral indicators of emotion to corroborate self-report data and for training study staff. Recruitment and data collection for Phase I will take place in Year 2. Recruitment and data collection for Phase II will begin in the 9th month of Year 2 and continue through Year 3. Additionally, in Year 3, data analyses will be started and an R01 application for a larger-scale efficacy trial examining the effect of countering EDBs on BPD symptoms will be submitted. A larger N will make possible longitudinal repeated-measurement of treatment mediators and exploration of moderators (e.g., severity). Finally, Year 4 will be used to complete data analyses, prepare manuscripts, and re-submit the R01 application.

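### The Phase II claim that medium effects are detectable is not supported for the weekly outcome, and for daily outcomes it rests on unstated assumptions; the randomization test's unit and reference set are not given

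*Combined protocol and SAP*

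**What the plan says.** All references are to the combined protocol and SAP.

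- **Randomization** (PHASE II: Multiple Baseline with Phase Change Procedures): "Participants (8) will be randomized to a 2- or 4-week initial baseline period". Everyone then receives four weekly sessions. The Study Overview adds four weeks of follow-up.
- **Sample size** (Power Analyses): observations are the unit. "Phase II will result in 88 observations for weekly measures and 616 observations for daily" measures, followed by "These numbers of observation will make possible detection of medium effect sizes across both phases".
- **Test** (Phase II Data Analyses): "We will also conduct non-parametric randomization tests of mean differences in EDBs, emotional intensity, and emotional tolerance as a function of phase". Results are read together with visual inspection. On the design the section adds: "By applying different baseline lengths across individuals, between-series comparisons will be possible".
- **Follow-up** (same section): "We will also explore maintenance effects of our intervention by examining stability in EDBs, emotional intensity, and emotional tolerance during the follow-up phase".
- **Daily data** (Phase II Assessment): "During all periods (baseline and intervention), participants will be asked to complete a daily log of EDBs and emotional intensity using SymTrend".
- **Dropout** (Participant Retention): "In both phases, participants that discontinue will be replaced".

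**The concern.** Counting person-weeks and person-days as the sample size says nothing about sensitivity until the effect metric, the error structure and the test are fixed. The plan fixes none of these. It does not say whether the randomization tests are run per person or pooled, or which reassignments form the reference set. It also does not say whether the two baseline lengths are allocated 4:4 or independently. The only randomized element is baseline length, so a test justified by that randomization has few possible outcomes.

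What is at stake is how a null result is read. MEAQ is collected weekly and is part of Phase II Hypothesis I. If it shows no change, the sensitivity statement invites the conclusion that a medium effect has been made unlikely. An undefined reference set also leaves the choice of test open after the data are seen.

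**Working it through.** **1. The plan's counts.** With four people on each baseline length, 4 × (2+4+4) + 4 × (4+4+4) = 40 + 48 = 88 weeks, and 88 × 7 = 616 days. Both figures reproduce. With k people on the 4-week baseline the weekly total is 80 + 2k. So 88 is exact only at k = 4, although it is also the expected total under independent 1:1 assignment.

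**2. What bears on baseline versus intervention.** Follow-up is 8 × 4 = 32 weeks (224 days). That leaves 88 − 32 = 56 weeks: baseline 4×2 + 4×4 = 24 and intervention 8×4 = 32. In days, 616 − 224 = 392 (168 and 224).

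**3. Weekly claim with all observations independent.** My assumptions are d = 0.5 and alpha 5%, with 80% power as benchmark; the plan states none of them. The two-sample t-test has noncentrality 0.5 × √(n₁n₂/(n₁+n₂)).

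| Comparison | Noncentrality | Two-sided | One-sided |
|---|---|---|---|
| Baseline v intervention, 24 v 32 | 1.85 | 44% | 57% |
| Baseline v all later weeks, 24 v 64 | 2.09 | 54% | 67% |
| Idealized equal split, 44 v 44 | 2.35 | 64% | 75% |
| Daily baseline v intervention, 168 v 224 | 4.90 | 99.8% | 99.9% |

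**4. Test based on the actual randomization.** One person has two possible assignments, so the smallest p is 1/2 = 0.50. Pooled over 8 people the reference set is C(8,4) = 70 if the split is fixed at 4:4 (smallest one-sided p 1/70 = 0.014). It is 2⁸ = 256 if assignment is independent (1/256 = 0.004).

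I used one workable statistic in a common six-week window: the sum over people of mean weeks 3-6 minus mean weeks 1-2 (2-week baseline), or mean weeks 5-6 minus mean weeks 1-4 (4-week baseline). For a prompt shift δ, a correctly scored person contributes δ. Scored with the wrong baseline length, the same person still contributes δ/2: δ − δ/2 for a true 2-week person, and δ/2 − 0 for a true 4-week person. The test therefore works on only half of the shift.

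Simulated power (one-sided 5%, immediate sustained shift, AR(1) errors, full compliance, one entry per day; ranges span 70 and 256 assignments):

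- Weekly, 0.5 within-person SD, autocorrelation 0-0.5: 16-20%. Using all eight weeks up to the end of intervention, with 70 assignments, gives 15-16%, so the window does not drive the result.
- Daily, 0.5 within-person SD: 56-60%, 39-43%, 30-32% and 22-25% at autocorrelation 0, 0.3, 0.5 and 0.7.
- Shift needed for 80% power: weekly about 1.5-1.8 within-person SD. Daily 0.65-0.71 SD at autocorrelation 0, 0.86-0.91 at 0.3 and 1.04-1.10 at 0.5.
- If change builds evenly over the four intervention weeks, weekly power at 2 SD is 8-10% in the six-week window and 19-20% in the eight-week window.

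**5. Where the weekly claim could hold.** Scale the medium effect to 0.5 total SD and remove person effects, so that within-person d = 0.5/√(1 − ICC), where ICC is the between-person share of variance. At 4:4 the information is 4 × (2×4/6) + 4 × (4×4/8) = 13.33, so noncentrality is d × √13.33 with 56 − 9 = 47 df. With independent residuals:

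| ICC | Within-person d | Two-sided | One-sided |
|---|---|---|---|
| 0.5 | 0.707 | 72% | 82% |
| 0.6 | 0.791 | 81% | 89% |
| 0.7 | 0.913 | 90% | 95% |

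On the same total-SD scale the pooled randomization test gives 24-30% weekly at ICC 0.5 and 34-43% at 0.7. The daily figures at ICC 0.5 are 82-85% at autocorrelation 0 and 47-52% at 0.5.

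**The case against.** The plan does not rest on one test. It foresees within-series comparisons as well as between-series ones, and step 5 shows that a person-adjusted contrast can exceed 80% weekly. Clustering is therefore not simply a penalty: for a within-person contrast, a large between-person share raises power if the effect is scaled to total SD. This stands. A reader might infer that Phase II cannot detect a medium weekly effect under any analysis. The documents do not support that, because they neither define the effect nor exclude such a model. Even the pooled test nears 80% if 90% of variance lies between people: within-person d is then 0.5/√0.1 = 1.58, inside the 1.5-1.8 range. But the plan states none of these conditions, and positive autocorrelation would generally lower the person-adjusted figures.

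A reader might also infer that the daily claim is wrong. It is not shown to be: it holds with independent days and in some autocorrelated cases. Entries are asked for at least once per day, each with two PANAS-X ratings, so 616 may understate the intensity data. On the other hand it assumes full compliance, where the plan cites 90% in similar studies.

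Two points are minor. The daily-log sentence says all periods and omits follow-up only in its parenthesis, and a 4:4 split is the natural reading of 88. Both call for clarification and neither is a substantive error. Finally, Phase II is preliminary, the tests are read with visual inspection, and no rule ties a null result to a conclusion. That limits the harm.

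**Conclusion.** The concern holds in limited form and should be fixed before data are seen. The weekly detection claim is not supported by the count offered for it: even with independence granted, d = 0.5 gives less than 80% power in every split tried, one- or two-sided. On the design's own randomization the sensitivity is far lower. Two-sided weekly power of 80% needs conditions such as a person-adjusted contrast, an effect scaled to total SD, roughly 60% or more of variance between people, and independent residuals. The daily claim is undetermined rather than refuted. The bar on per-person p-values from the baseline-length randomization is exact and needs no assumption. The other figures depend on d = 0.5, 5% alpha and the 80% benchmark, and the pooled-test figures also on a prompt change and AR(1) errors.

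**What to change.** 1. Remove the medium-effect sentence for Phase II, or replace it with what the chosen test can detect, stating alpha, sidedness, effect metric and autocorrelation. For the pooled test, one-sided 5% with prompt change, 80% power needs about 1.5-1.8 within-person SD weekly and about 0.65-0.9 SD daily at autocorrelation 0.3 or less.
2. State that the randomization test is pooled over the 8 participants. Give the allocation rule, including how replacements are assigned, and the reference set that follows: 70 assignments if fixed 4:4, which matches the 88, or 256 if independent. Name the statistic before data are seen. The six-week statistic is one option, not a requirement: it needs no follow-up data, but it leaves weeks 7-8 of the 4-week-baseline participants untested and has little power for gradual change.
3. Do not base per-person p-values on the baseline-length randomization. Report individual changes as plots and effect sizes.
4. Reconcile the periods named for daily logs in Phase II Assessment with the follow-up analysis in Phase II Data Analyses and with the 616, which includes 224 follow-up days.

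The cost is wording and a short script, with no added participants or visits. The sensitivity statement becomes less favourable and individual p-values are given up.
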